## 7. Discontinuation of Study Intervention and Participant Discontinuation/Withdrawal

Discontinuation of specific sites or of the study as a whole are handled as part of Section 10.1, Appendix 1.

### 7.1. Discontinuation of Study Intervention

When necessary, a participant may be permanently discontinued from study intervention. If so, the participant will remain in the study and follow procedures for remaining study visits, as shown in the SoA.

A participant who prematurely discontinues study intervention is strongly encouraged to remain in the study for safety and efficacy assessments through the treatment period and post-treatment follow-up.

If a participant who discontinues the double-blind study treatment prematurely declines to complete the remaining scheduled study visits, then the participant should complete the early ED procedures indicated in the SoA. Participants should be encouraged to come back for the last treatment visit (Visit 11) to complete the end-of-treatment phase procedures and return for the post-treatment follow-up Visit 801.

Possible reasons leading to permanent discontinuation of study intervention:

- **participant decision**
  - the participant requests to discontinue study intervention
- **clinical considerations**
  - initiation of a prohibited medication (Section 6.8.2), if participants will not or cannot discontinue them
  - BMI  $\leq 18.5 \text{ kg/m}^2$  is reached at any time during the treatment period, study intervention discontinuation should be considered
  - TEAE
    - intolerable GI symptoms despite management (Section 6.5.1)  
*Note:* The investigator should contact the Sponsor CRP to discuss whether it is medically appropriate for the participant to continue study treatment.
    - significant elevation of calcitonin

- If the investigator determines that a systemic hypersensitivity reaction has occurred related to study intervention administration, the participant may be permanently discontinued from the study intervention, and the sponsor's designated medical monitor should be notified. If the investigator is uncertain about whether a systemic hypersensitivity reaction has occurred and whether discontinuation of study intervention is warranted, the investigator may consult the sponsor
- occurrence of any other TEAE, SAE, or clinically significant finding for which the investigator believes that permanent study intervention discontinuation is the appropriate measure to be taken
- Diagnosis of
  - T1DM
  - Thyroid C-cell hyperplasia, MTC or MEN Syndrome type 2 after randomization
  - acute or chronic pancreatitis
  - an active or untreated malignancy (other than basal or squamous cell skin cancer, in situ carcinomas of the cervix, or in situ prostate cancer) after randomization
- onset of pregnancy in a female participant (see Sections 7.2 and 8.3.2)
- Suicidal Ideation and Behavior
  - PHQ-9 score  $\geq 15$ 
    - Participants should be referred to a Mental Health Professional (MHP) to assist in deciding whether the participant should be discontinued from study intervention. If a participant's psychiatric disorder can be adequately treated with psycho- and/or pharmacotherapy, then the participant, at the discretion of the Investigator (in agreement with the MHP), may be continued in the trial on randomly assigned therapy.
    - in addition, study intervention may be discontinued if participants:
      - answered "yes" to Question 4 or Question 5 on the "Suicidal Ideation" portion of the C-SSRS, **or**
      - answered "yes" to any of the suicide-related behaviors on the Suicidal Behavior portion of the C-SSRS.

A psychiatrist or appropriately trained professional may assist in the decision to discontinue the participant. The participant should be referred to a MHP for further evaluation and care.

### 7.1.1. Liver Chemistry Stopping Criteria

The study intervention should be interrupted or discontinued if one or more of these conditions occur:

Elevation	Exception
ALT or AST >8x ULN	
ALT or AST >5x ULN for more than 2 weeks	
ALT or AST >3x ULN and either TBL >2x ULN or INR >1.5	In participants with Gilbert's syndrome, doubling of direct bilirubin should be used for drug interruption/ discontinuation decisions rather than TBL>2x ULN.
ALT or AST >3x ULN with the appearance of fatigue, nausea, vomiting, right upper quadrant pain or tenderness, fever, rash, and/or eosinophilia (>5%)	
ALP >3x ULN, when the source of increased ALP is the liver	
ALP >2.5x ULN and TBL > 2x ULN	In participants with Gilbert's syndrome, doubling of direct bilirubin should be used for drug interruption/ discontinuation decisions rather than TBL>2x ULN.
ALP >2.5x ULN with the appearance of fatigue, nausea, vomiting, right upper quadrant pain or tenderness, fever, rash, and/or eosinophilia (>5%)	

Source: FDA 2009 and other consensus guidelines, with minor modifications

Abbreviations: ALT = alanine aminotransferase; AST = aspartate aminotransferase; ALP = alkaline phosphatase; INR = international normalized ratio; TBL = total bilirubin level; ULN = upper limit of normal.

Resumption of the study intervention can be considered only in consultation with the Lilly-designated medical monitor and only if the liver test results return to baseline and if a self-limited non-drug etiology is identified.

Participants who are discontinued from study intervention due to a hepatic event or liver test abnormality should have additional hepatic safety data collected as described in Section 10.6, Appendix 6.

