## 10.6. Appendix 6: Liver Safety: Suggested Actions and Follow-up Assessments

### 10.6.1. Hepatic Evaluation Testing

See Sections 10.6.2 and 10.6.3, Appendix 6 for guidance on appropriate test selection.

The Lilly-designated central laboratory must complete the analysis of all selected testing except for microbiology testing.

Local testing may be performed *in addition to central testing* when necessary for immediate participant management.

Results will be reported if a validated test or calculation is available.

Hematology	Clinical Chemistry
Hemoglobin	Total bilirubin
Hematocrit	Direct bilirubin
Erythrocytes (RBCs – red blood cells)	Alkaline phosphatase (ALP)
Leukocytes (WBCs – white blood cells)	Alanine aminotransferase (ALT)
Differential:	Aspartate aminotransferase (AST)
Neutrophils, segmented	Gamma-glutamyl transferase (GGT)
Lymphocytes	Creatine kinase (CK)
Monocytes	Other Chemistry
Basophils	Acetaminophen
Eosinophils	Acetaminophen protein adducts
Platelets	Alkaline phosphatase isoenzymes
Cell morphology (RBC and WBC)	Ceruloplasmin
	Copper
Coagulation	Ethyl alcohol (EtOH) (quantitative)
Prothrombin time, INR (PT-INR)	Haptoglobin
Serology	Immunoglobulin A (IgA) (quantitative)
Hepatitis A virus (HAV) testing:	Immunoglobulin G (IgG) (quantitative)
HAV total antibody	Immunoglobulin M (IgM) (quantitative)
HAV IgM antibody	Phosphatidylethanol (Peth)
Hepatitis B virus (HBV) testing:	Urine Chemistry
Hepatitis B surface antigen (HbsAg)	Drug screen
Hepatitis B surface antibody (anti-HBs)	Ethyl glucuronide (EtG)
Hepatitis B core total antibody (anti-HBc)	Other Serology
Hepatitis B core IgM antibody	Anti-nuclear antibody (ANA)

Hepatitis B core IgG antibody	Anti-smooth muscle antibody (ASMA) a
HBV DNA b	Anti-actin antibody c
Hepatitis C virus (HCV) testing:	Epstein-Barr virus (EBV) testing:
HCV antibody	EBV antibody
HCV RNA b	EBV DNA b
Hepatitis D virus (HDV) testing:	Cytomegalovirus (CMV) testing:
HDV antibody	CMV antibody
Hepatitis E virus (HEV) testing:	CMV DNA b
HEV IgG antibody	Herpes simplex virus (HSV) testing:
HEV IgM antibody	HSV (Type 1 and 2) antibody
HEV RNA b	HSV (Type 1 and 2) DNA b
Microbiologyd	Liver kidney microsomal type 1 (LKM-1) antibody
Culture:	
Blood	
Urine	

a Not required if anti-actin antibody is tested.

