### 10.6.2. Close Hepatic Monitoring

Laboratory tests (Section 10.2, Appendix 2), including ALT, AST, ALP, TBL, direct bilirubin, gamma-glutamyl transferase, and creatine kinase, should be repeated within 48 to 72 hours to confirm the abnormality and to determine if it is increasing or decreasing, if one or more of these conditions occur:

If a participant with baseline results of...	develops the following elevations:
ALT or AST <1.5x ULN	ALT or AST $\geq$ 3x ULN
ALP <1.5x ULN	ALP $\geq$ 2x ULN
TBL <1.5x ULN	TBL $\geq$ 2x ULN (except for participants with Gilbert's syndrome)
ALT or AST $\geq$ 1.5x ULN	ALT or AST $\geq$ 2x baseline
ALP $\geq$ 1.5x ULN	ALP $\geq$ 2x baseline
TBL $\geq$ 1.5x ULN	TBL $\geq$ 1.5x baseline (except for participants with Gilbert's syndrome)

Abbreviations: ALP = alkaline phosphatase; ALT = alanine aminotransferase; AST = aspartate aminotransferase; TBL = total bilirubin level; ULN = upper limit of normal.

If the abnormality persists or worsens, clinical and laboratory monitoring, and evaluation for possible causes of abnormal liver tests should be initiated by the investigator in consultation with the Lilly-designated medical monitor. At a minimum, this evaluation should include physical examination and a thorough medical history, including symptoms, recent illnesses (for example, heart failure, systemic infection, hypotension, or seizures), recent travel, history of concomitant medications (including over-the-counter), herbal and dietary supplements, history of alcohol drinking and other substance abuse.

Initially, monitoring of symptoms and hepatic biochemical tests should be done at a frequency of 1 to 3 times weekly, based on the participant's clinical condition and hepatic biochemical tests. Subsequently, the frequency of monitoring may be lowered to once every 1 to 2 weeks, if the participant's clinical condition and lab results stabilize. Monitoring of ALT, AST, ALP, and total bilirubin level should continue until levels normalize or return to approximate baseline levels.

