### 10.6.3. Comprehensive Hepatic Evaluation

A comprehensive evaluation should be performed to search for possible causes of liver injury if one or more of these conditions occur:

If a participant with baseline results of...	develops the following elevations:
ALT or AST <1.5x ULN	ALT or AST $\geq 3x$ ULN with hepatic signs/symptoms a , or ALT or AST $\geq 5x$ ULN
ALP <1.5x ULN	ALP $\geq 3x$ ULN
TBL <1.5x ULN	TBL $\geq 2x$ ULN (except for participants with Gilbert's syndrome)
ALT or AST $\geq 1.5x$ ULN	ALT or AST $\geq 2x$ baseline with hepatic signs/symptoms a , or ALT or AST $\geq 3x$ baseline
ALP $\geq 1.5x$ ULN	ALP $\geq 2x$ baseline
TBL $\geq 1.5x$ ULN	TBL $\geq 2x$ baseline (except for participants with Gilbert's syndrome)

Abbreviations: ALP = alkaline phosphatase; ALT= alanine aminotransaminase; AST = aspartate aminotransferase;

TBL = total bilirubin level; ULN = upper limit of normal.

a Hepatic signs/symptoms are severe fatigue, nausea, vomiting, right upper quadrant abdominal pain, fever, rash, and/or eosinophilia >5%.

At a minimum, this evaluation should include physical examination and a thorough medical history, as outlined above, as well as tests for PT-INR; tests for viral hepatitis A, B, C, or E; tests for autoimmune hepatitis; and an abdominal imaging study (for example, ultrasound or CT scan).

Based on the participant's history and initial results, further testing should be considered in consultation with the Lilly-designated medical monitor, including tests for hepatitis D virus , cytomegalovirus , Epstein-Barr virus , acetaminophen levels, acetaminophen protein adducts, urine toxicology screen, Wilson's disease, blood alcohol levels, urinary ethyl glucuronide, and blood phosphatidylethanol. Based on the circumstances and the investigator's assessment of the participant's clinical condition, the investigator should consider referring the participant for a hepatologist or gastroenterologist consultation, magnetic resonance cholangiopancreatography, endoscopic retrograde cholangiopancreatography, cardiac echocardiogram, or a liver biopsy.

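### INR >1.5 is a liver stopping criterion at ALT/AST >3x ULN, but no named test supplies an INR until the comprehensive hepatic evaluation: a minor gap that is cheap to narrow

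*Protocol*

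**What the plan says.** Protocol Section 7.1.1 lists the conditions under which study drug should be interrupted or discontinued. One row reads "ALT or AST >3x ULN and either TBL >2x ULN or INR >1.5", so INR is an alternative to bilirubin and can meet the row without it. The only exception given for that row concerns bilirubin in Gilbert's syndrome.

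Section 10.6.2 governs close hepatic monitoring. It has three steps:

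- **Repeat.** Laboratory tests, "including ALT, AST, ALP, TBL, direct bilirubin, gamma-glutamyl transferase, and creatine kinase, should be repeated within 48 to 72 hours".
- **Evaluation if the abnormality persists or worsens.** The "evaluation for possible causes of abnormal liver tests should be initiated by the investigator in consultation with the Lilly-designated medical monitor". Its floor is clinical: "At a minimum, this evaluation should include physical examination and a thorough medical history, including symptoms, recent illnesses".
- **Continued monitoring.** "Initially, monitoring of symptoms and hepatic biochemical tests should be done at a frequency of 1 to 3 times weekly", and "Monitoring of ALT, AST, ALP, and total bilirubin level should continue until levels normalize or return to approximate baseline levels".

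Section 10.6.3, the comprehensive evaluation, is where coagulation testing enters as a minimum: "as well as tests for PT-INR; tests for viral hepatitis A, B, C, or E".

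PT-INR is on the Section 10.6.1 hepatic test list, which the central laboratory analyses, but that section sends the reader to 10.6.2 and 10.6.3 to decide which tests to select. The Schedule of Activities and Appendix 2 (Section 10.2) contain no coagulation test.

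**The concern.** A stopping criterion can act only if its input is measured. A site could carry out every named step and keep dosing a participant who meets a written stopping rule. An example is a participant with normal baseline ALT, on-study ALT of 4x ULN, normal bilirubin, no symptoms and an INR above 1.5. Such a participant would be monitored closely, yet none of the tests named at that stage would show the one abnormality that calls for stopping. What is at stake is individual safety in a narrow set of cases. No efficacy endpoint or analysis is touched.

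**Working it through.** The plan gives no figure to reproduce, so the check sets the thresholds side by side.

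**Inputs** (b is the baseline of the enzyme concerned, in multiples of ULN)

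- The INR row applies above 3x ULN, and a separate row stops drug above 8x ULN (Section 7.1.1).
- Repeat trigger r: 3 if b <1.5, otherwise 2b (Section 10.6.2).
- Trigger i for PT-INR without symptoms: 5 if b <1.5, otherwise 3b (Section 10.6.3).
- Largest baseline considered: b = 3, the ALT entry limit (Section 5.2, criterion 33).

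**Conditions held fixed:** no hepatic signs or symptoms, TBL <2x ULN, ALP <3x ULN, and the other enzyme not itself at a 10.6.3 trigger.

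**Formulas**

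- Upper end of the range with no INR named: u = min(i, 8).
- Gap width = u − 3.
- Part covered if PT-INR is added at the 10.6.2 repeat = u − r.
- Part left = r − 3.

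| Baseline b | r | i | u | Range with no INR named | Width | Covered by fix | Left |
|---|---|---|---|---|---|---|---|
| <1.5 | 3 | 5 | 5 | >3x to <5x | 5 − 3 = 2 | 5 − 3 = 2 | 0 |
| 1.5 | 3 | 4.5 | 4.5 | >3x to <4.5x | 4.5 − 3 = 1.5 | 4.5 − 3 = 1.5 | 0 |
| 2 | 4 | 6 | 6 | >3x to <6x | 6 − 3 = 3 | 6 − 4 = 2 (67%) | 4 − 3 = 1 |
| 3 | 6 | 9 | 8 | >3x to 8x | 8 − 3 = 5 | 8 − 6 = 2 (40%) | 6 − 3 = 3 |

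Widths are multiples of ULN, not probabilities; the documents give no distribution of baseline ALT or AST. At baselines of 2x and 3x, the row for values above 5x ULN lasting more than two weeks also stops drug when such values persist.

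**Where the gap sits.** Take baseline <1.5x ULN and an on-study value >3x to <5x ULN. Section 10.6.3 is then reached only through hepatic signs or symptoms, TBL >=2x ULN or ALP >=3x ULN. In nearly all those cases another row of 7.1.1 already stops drug: the symptom row, the bilirubin alternative, or the hepatic ALP row. The exceptions are narrow: a value exactly at a threshold, Gilbert's syndrome, or ALP that does not come from the liver. In this range INR is therefore named mostly when the decision no longer needs it. It is not named when it is the only part of the >3x criterion that could still act.

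**Does the open-ended wording supply the test?** The 10.6.2 repeat list is not exhaustive, but it refers to Appendix 2, which has no INR. The same list names gamma-glutamyl transferase, which is also absent from Appendix 2. So 10.6.2 does go beyond the routine panel by name where that is wanted, and INR is not among those names.

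**The case against.** The case against is substantial.

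- **INR is available and prompted.** Section 7.1.1 names it, so an investigator applying that row is told it matters. It is on the 10.6.1 list, the 10.6.2 list is open-ended, Appendix 2 allows additional tests at any time, and Appendix 6 is titled "Liver Safety: Suggested Actions and Follow-up Assessments".
- **Other safeguards apply.** Section 8.2.4 calls for clinically significant abnormal results to be repeated and, if they do not resolve, for the cause to be found and the sponsor told. Section 7.1 permits discontinuation for any clinically significant finding. The symptom row of 7.1.1 works without INR, and Section 4.3 reports that most adverse events with this drug are gastrointestinal, mainly nausea, vomiting and diarrhea; the row lists nausea and vomiting.
- **Adding INR has a side effect.** Anticoagulants are neither excluded (Section 5.2) nor prohibited (Section 6.8.2), and the INR row has no exception for them. A therapeutic INR with ALT just above 3x ULN would meet the rule for reasons unrelated to the liver.
- **The remedy is partial** where the gap is widest, as the table shows.
- **The laboratory manual**, which Section 8.2.4 requires sites to follow, may already provide for the test.

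The first two arguments show that the gap is small. They do not close it, because permission to order a test does not assure that it is ordered. The third stands and changes the fix. The fourth stands as a stated limit. The fifth cannot be checked from the protocol and SAP.

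A reader might infer that participants in this range go unsupervised, or that the stopping rule is defective as a whole. The documents do not support either reading. Section 10.6.2 calls for an early repeat and, if the abnormality persists or worsens, medical monitor involvement and frequent testing. The bilirubin, symptom, >8x and sustained >5x rows all work without an INR.

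**Conclusion.** The point holds as a minor safety improvement, not as the correction of an error. The INR criterion is not assured to be evaluated in a participant without symptoms who has TBL <2x ULN and ALP <3x ULN:

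- baseline ALT/AST <1.5x ULN: from >3x to <5x ULN;
- baseline >=1.5x ULN: from >3x ULN up to 3x baseline, capped by the >8x ULN stop.

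The exposure is an isolated raised INR that nobody orders. The documents give no frequency. That it is likely rare is a judgement, not a figure.

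The conclusion rests on one assumption: that neither the ISAs nor the laboratory manual, which are not among the documents, names INR at the 10.6.2 repeat. If either does, the point falls.

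**What to change.** 1. In Section 10.6.2, name PT-INR among the 48 to 72 hour repeat tests when ALT or AST is the trigger.
2. Cross-reference this in the INR row of Section 7.1.1.
3. Add an exception to that row for an INR explained by anticoagulant therapy, decided with the medical monitor, for example against the participant's pre-event INR. The Schedule of Activities collects no INR, so that earlier value would have to come from the participant's own care.

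**Cost.** Protocol wording, one assay already on the central hepatic list, and possibly one more tube, on a redraw already called for. There is no new visit and no new trigger. INR values in anticoagulated participants will need interpretation.

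**What remains.** For baselines above 1.5x ULN, a gap stays open from >3x ULN to 2x baseline, because the 10.6.2 triggers are left unchanged. Closing it would need a separate PT-INR trigger at >3x ULN whatever the baseline. Leaving it open is the price of keeping the protocol's baseline-relative monitoring.

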### 7.1.2. Temporary Discontinuation

In certain situations, after randomization, the investigator may need to temporarily interrupt study intervention. Every effort should be made by the investigator to maintain participants on study intervention and to restart study intervention after any temporary interruption, as soon as it is safe to do so. Distribution of study intervention at the correct dose will be per IWRS instructions.

Investigators should inform the sponsor that study intervention has been temporarily interrupted. The data related to temporary interruption of study treatment will be documented in source documents and entered on the CRF.

If study intervention interruption is...	then...
2 consecutive doses or less	participant restarts study intervention at last administered dose, as per escalation schedule.
3 consecutive doses or more	participant restarts study intervention (at 5 mg, managed by IWRS) and repeats dose escalation scheme.
Due to an AE	the event is to be documented and followed according to the procedures in Section 8.3 of this protocol.
Due to intolerable persistent GI AE	participants should be treated as suggested in Section 6.5.1 .

Abbreviations: AE = adverse event; GI = gastrointestinal; IWRS = interactive web-response system.

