#### **4.3. Justification for Dose**

Tirzepatide doses of up to 15 mg administered SC QW will be evaluated in this study. Participants may be treated with lower maintenance dose of 10 mg if they do not achieve full dose escalation to 15 mg and/or do not tolerate 15 mg.

These doses and associated escalation schemes were selected based on assessment of safety, efficacy (weight loss), and GI tolerability data in Phase 1, 2, and 3 studies in patients with T2DM, followed by exposure-response modeling of the data that predicted weight loss in patients with overweight or obesity.

Dosing algorithms starting at a low dose of 2.5 mg accompanied by dose escalation of 2.5 mg increments every 4 weeks should permit time for development of tolerance to GI events and are predicted to minimize GI tolerability concerns.

Similar to the GLP-1RA class, most of the tirzepatide AEs were dose-dependent and GI-related, consisting mainly of nausea, vomiting, and diarrhea. In general, these events were mild or moderate in severity, with few severe episodes, and transient.

Tirzepatide doses of 10 mg and 15 mg as MTD were selected based principally on the following criteria:

- each dose provides robust weight loss relative to placebo
- the percent of participants achieving  $\geq 10\%$  weight loss is higher with 15 mg than 10 mg, and
- safety and tolerability were supported by Phase 3 results in T2DM.

The proposed tirzepatide maintenance dose of up to 15 mg using a dose-escalation regimen is expected to safely maximize the potential for weight loss while minimizing GI tolerability concerns as has been achieved for approved GLP-1 RA drugs. The subsequent benefit of weight loss should result in clinically meaningful improvements in AHI.

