#### 6.5.1. Management of Participants with Gastrointestinal Symptoms

In participants who experience intolerable GI symptoms (for example, nausea, vomiting, or diarrhea) at any time during the study, the following measures are recommended:

- counselling on dietary behaviors that may help mitigate nausea and vomiting, (for example, eating smaller meals, splitting 3 daily meals into 4 or more smaller ones, and stopping eating when they feel full).
- if symptoms persist despite #1, prescribing symptomatic medication (for example, antiemetic or antidiarrheal medication), at the investigator's discretion.
- if symptoms persist despite #1 and #2, interrupting study intervention for 1 dose, provided the participant has taken the last 3 weekly doses. Study treatment should be resumed at the assigned dose immediately, either alone or in combination with symptomatic medication, which can also be utilized to manage symptoms (Section 6.8).

During the first 24 weeks of the treatment period (20-week dose escalation plus 4 weeks), participants unable to tolerate 2.5 mg or 5 mg (despite the interventions mentioned above) will be discontinued from the study intervention but remain in the study.

For participants unable to tolerate any dose between 7.5 mg and 15 mg inclusive, despite the above measures, the investigator should contact Lilly to consider a dose de-escalation step with subsequent re-escalation by 2.5 mg every 4 weeks in a blinded fashion, to reach either the 10-mg or 15-mg dose as described below.

Only 1 cycle of dose de-escalation and re-escalation is permitted during the first 24 weeks of the treatment period. MTD is either 10 mg or 15 mg. Dose modifications after the first 24 weeks of the treatment period are not permitted. For temporary study treatment discontinuation, see Section 7.1.2.

Participants who tolerate

- 10 mg, but do not tolerate 12.5 mg or 15 mg even following the above measures, including 1 de-escalation and re-escalation attempt, will continue on 10 mg as their MTD dose.
- 12.5 mg, but do not tolerate 15 mg even after the above measures, including 1 de-escalation and re-escalation attempt, will continue on 10 mg as their MTD dose.
- 15 mg will continue on 15 mg as their MTD dose.

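### The 5 mg restart after three or more missed doses does not fit the 2.5 mg start of the escalation scheme for participants who have taken only 2.5 mg

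*Protocol*

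**What the plan says.** Four places in the protocol bear on this.

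- Section 4.3 (Justification for Dose) describes the scheme as "Dosing algorithms starting at a low dose of 2.5 mg accompanied by dose escalation of 2.5 mg increments every 4 weeks", and gives the purpose: this "should permit time for development of tolerance to GI events".
- Section 6.5.1 (Management of Participants with Gastrointestinal Symptoms) gives the length: "During the first 24 weeks of the treatment period (20-week dose escalation plus 4 weeks". It also treats 2.5 mg as a dose that participants actually take, since it has a rule for "participants unable to tolerate 2.5 mg or 5 mg".
- Section 7.1.2 (Temporary Discontinuation), row for two or fewer consecutive missed doses: "participant restarts study intervention at last administered dose, as per escalation schedule".
- Section 7.1.2, row for three or more: "participant restarts study intervention (at 5 mg, managed by IWRS) and repeats dose escalation scheme".

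Section 7.1.2 also says that "Distribution of study intervention at the correct dose will be per IWRS instructions". Neither the protocol nor the SAP text limits the 5 mg restart to participants who had already reached 5 mg.

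**The concern.** The three-or-more row names one restart dose whatever step the participant had reached. For someone still on the first step, that dose is higher than any they have taken. It also does not match the instruction to repeat the escalation, because the scheme in Section 4.3 begins at 2.5 mg. And it sits oddly beside the row above it, which returns the participant to the dose last taken.

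At stake is a dosing instruction that sites and the IWRS must carry out. For this group the sections cannot all be followed to the letter, so a site could not tell from the protocol whether a 5 mg assignment after an early interruption is intended or is a gap in the drafting.

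**Working it through.** No sample-size or power calculation applies. The check lists the weekly doses and applies the two restart rows to them.

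**Escalation length.** Inputs: 2.5 mg start and 2.5 mg steps every 4 weeks (Section 4.3), top dose 15 mg. The steps before 15 mg are 2.5, 5, 7.5, 10 and 12.5 mg, which is 5 steps. 5 × 4 = 20 weeks, and 20 + 4 = 24 weeks. Both figures in Section 6.5.1 reproduce, and the 20 weeks includes a full 4-week step at 2.5 mg. The schedule is therefore 2.5 mg at Weeks 0 to 3, 5 mg from Week 4 and 7.5 mg from Week 8.

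**Restart rows applied to participants who have taken only 2.5 mg.** The first dose is at Week 0 (Visit 2 in the Schedule of Activities). With k doses taken and then m missed, the restart falls at Week k + m.

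| 2.5 mg doses taken | Weeks missed | Restart week | Restart dose, Section 7.1.2 | Highest dose taken | Scheduled dose that week |
|---|---|---|---|---|---|
| 1 | 1–2 | 3 | 2.5 mg | 2.5 mg | 2.5 mg |
| 1 | 1–3 | 4 | 5 mg | 2.5 mg | 5 mg |
| 2 | 2–3 | 4 | 2.5 mg | 2.5 mg | 5 mg |
| 2 | 2–4 | 5 | 5 mg | 2.5 mg | 5 mg |
| 3 | 3–4 | 5 | 2.5 mg | 2.5 mg | 5 mg |
| 3 | 3–5 | 6 | 5 mg | 2.5 mg | 5 mg |
| 4 | 4–5 | 6 | 2.5 mg | 2.5 mg | 5 mg |
| 4 | 4–6 | 7 | 5 mg | 2.5 mg | 5 mg |

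**What the table shows.**

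1. In each pair, two missed doses lead back to 2.5 mg and three lead to 5 mg. The longer gap gives the higher restart dose.
2. With one to three doses taken, the first step is cut short by 4 − k doses, that is by 3, 2 or 1. At the extreme, 5 mg follows a single 2.5 mg dose.
3. With all four doses taken, nothing is skipped (4 − 4 = 0), but 5 mg is still above any dose taken.
4. The earliest restart after three missed doses is Week 1 + 3 = 4, when 5 mg is already scheduled. No restart in the table is ahead of the calendar.
5. Once a single 5 mg dose has been taken, the restart dose no longer exceeds the highest prior dose and the conflict disappears.

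**The case against.** The best defence has three parts.

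First, Section 4.3 explains how treatment starts; it is not a re-entry rule. Section 7.1.2 can be read as telling participants to rejoin the scheme at 5 mg, without claiming that the scheme begins there. This is a fair reading of the word used for repeating, but it does not explain why the two adjacent rows move in opposite directions for someone on 2.5 mg.

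Second, the restart comes no earlier than Week 4, and 2.5 to 5 mg is one ordinary increment. This stands. A reader might infer that the rule forces a step up that the plan never intended, or point out that 5 mg is twice the highest dose received. The documents do not support reading that as an excess: every adherent participant makes the same doubling, 5 / 2.5 = 2, at Week 4.

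Third, the dose is assigned by the IWRS, and an exception may be written into its rules, the ISAs or the schema figure in Section 1.2. None of these was available. This also stands, and it limits what can be said about what would happen in practice.

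A reader might also infer that early interruptions are mostly gastrointestinal, so that the rule acts on the participants least able to take a higher dose. The documents give no frequencies, and their own route points the other way. Section 7.1.2 sends persistent gastrointestinal cases to Section 6.5.1, where the pause is "interrupting study intervention for 1 dose, provided the participant has taken the last 3 weekly doses". That route does not produce a three-dose gap. Longer gaps would come from other causes, such as the liver-test interruptions in Section 7.1.1 or supply disruption under Appendix 9.

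**Conclusion.** The inconsistency is real and minor. Section 7.1.2 states a dosing rule that, followed literally, disagrees with the escalation scheme in Sections 4.3 and 6.5.1 and with its own adjacent row, for tirzepatide participants who have taken only 2.5 mg. Placebo participants have no dose level and are not affected in this way.

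The documents do not give the number affected, and it cannot be derived from them. It is probably small, because it requires at least three consecutive missed doses before any 5 mg dose has been taken. A reader might go on to infer extra discontinuations in the active arm and an effect on the efficacy estimand. Nothing in the protocol or SAP gives a count, rate or range for that, so no such claim is made.

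The conclusion assumes that the two-or-fewer row means the dose last taken, which is its plain wording. If its closing reference to the escalation schedule were meant to move participants to the calendar dose, the contrast between the rows would weaken. The mismatch between a 5 mg restart and a scheme that begins at 2.5 mg would remain. The conclusion also assumes that no exception exists in the material not seen.

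**What to change.** The sponsor should reconcile Sections 4.3, 6.5.1 and 7.1.2 so that they state one consistent rule for participants who have not yet reached the named restart dose. If the two rows of Section 7.1.2 are meant to differ for this group, the text should say so. The sponsor should also confirm that the IWRS rule, and any related text in the ISAs and the schema, match. Which dose applies is the sponsor's decision, and none is proposed here.

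The cost is a short protocol clarification and a check of the IWRS specification. No analysis or sample-size figure changes.
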